19. PUBLICATION

All information concerning the product as well as any information such as clinical indications for the study drugs, their formula, their formulation, methods of manufacture and other scientific data relating to it, that have been provided by CSPC Pharma or designee, and are unpublished, are confidential and must remain the sole property of CSPC Pharma.

The Investigator will agree to use the information only for the purposes of carrying out this study and for no other purpose unless prior written permission from CSPC Pharma is obtained. CSPC Pharma has full ownership of the CRFs completed as part of the study.

By signing the study protocol, the Investigator agrees that the results of the study may be used for the purposes of national and international registration, publication, and information for medical and pharmaceutical professionals by CSPC Pharma. If necessary, the authorities will be notified of the Investigator's name, address, qualifications, and extent of involvement.

CSPC Pharma or designee will prepare a final report on the study. The Investigator may not publish or present any information on this study without first presenting the information to CSPC Pharma for review.

APPENDIX A. LABORATORY ASSESSMENTS

Hematology	Clinical Chemistry	Urinalysis
Hemoglobin (Hgb)	Blood urea nitrogen (BUN)	pН
Hematocrit (Hct)	Creatinine	Specific gravity
Platelet count	Total bilirubin	Protein
Red blood cell (RBC) count	Alkaline phosphatase	Glucose
White blood cell (WBC) count	Aspartate transaminase (AST)	Ketones
with differential	Alanine transaminase (ALT)	Bilirubin
	Gamma-glutamyl	Blood
	transferase (GGT)	Nitrites
	Lactic dehydrogenase (LDH)	Leukocytes
	Glucose	Urobilinogen
	Albumin	Microscopic urine analysis
Alcohol test	Total protein	
	Bicarbonate	
	Phosphate	
	Sodium	
	Potassium	
	Chloride	
	Calcium	
	Total cholesterol	
	Urate	
Urine Drug Screen	Serology Screen	
Amphetamines	Human immunodeficiency	
Barbiturates	virus (HIV)	
Cannabinoids	Hepatitis B surface	
Cocaine metabolites	antigen (HBsAg)	
Opiates	Hepatitis C virus (HCV)	
Benzodiazepines		
Methamphetamine	Other	

Pregnancy test

BMI	body mass index
BUN	Blood urea nitrogen
C _{max}	Maximum concentration
CRF	Case report form
CRU	Clinical research unit
CS	Clinically significant
CSPC Pharma	CSPC Pharmaceutical Co., Ltd.
CSR	Clinical Study Report
CVB	between-subject coefficients of variation
CVw	within-subject coefficients of variation
ECG	Electrocardiography
GGT	Gamma-glutamyl transferase
Hct	Hematocrit
Hgb	Hemoglobin
LDH	Lactic dehydrogenase
MedDRA	Medical Dictionary for Regulatory Activities
NCS	Not clinically significant
PK	Pharmacokinetic(s)
QTcB	Bazett's QT correction
QTcF	Fridericia's QT correction
R	Reference product
RAND	Randomized Population
RBC	Red blood cell
SAE	Serious adverse event
SAF	Safety Population
SAP	statistical analysis plan
SCRN	Screened Population
SD	standard deviation
T	Test product
TEAE	Treatment-emergent AEs
TFLs	Tables, Figures, and Listings
WBC	White blood cell
WHO-DD	World Health Organization-Drug Dictionary

1 INTRODUCTION

This statistical analysis plan (SAP) describes the final statistical analysis for subject information and safety data to be done for the study entitled "A Randomized, Open-label, Single-Dose, Two-Way Crossover Study to Assess the Relative Bioavailability of 5 mg of Levamlodipine Maleate Tablets versus 10 mg of Amlodipine Besylate Tablet (NORVASC® from Pfizer Inc.) in Healthy Subjects Followed by a Phase to Study Food Effect on the PK Profile of Levamlodipine" (V2.0 21MAY2018). All planned PK analyses will be described in a separate PK analysis plan. Mock shells are also produced as a separate working document to facilitate programming of Tables, Figures, and Listings (TFLs) according to finalized SAP. The SAP is to be interpreted in conjunction with the protocol, and supersedes the statistical considerations identified in the protocol. If the final clinical study report contains changes to any planned statistical analyses, the justification for any such differences will be fully documented in the CSR.

1.1 Study Objectives

See protocol section 4.

1.2 Study Design

This study consists of 2 parts:

Part 1 will be a randomized, open-label, single-dose, two-way crossover study to assess the relative BA of 5 mg of levamlodipine maleate tablets from CSPC (Test Product) versus 10 mg of Amlodipine Besylate Tablet NORVASC® from Pfizer Inc. (Reference Product) after a single oral administration under fasted conditions in male and female healthy subjects. Approximately 32 healthy volunteers will be enrolled to obtain 27 completed subjects. Eligible subject will be randomized to receive one of two treatment sequences (RT or TR; R=10 mg of NORVASC® and T=5 mg of levamlodipine maleate tablets). Eligible subjects will be admitted to the clinical research center (CRU) within 24 hours before baseline assessments in Period 1 and will stay at the CRU for 3 nights. A single dose of study drug should be taken orally with 240 ml (about 8 fluid ounces) of water at site after being fasted overnight, and meal will be allowed around 1 hour after dosing. Subjects should return to the CRU on Days 4 till 8 to provide PK samples and to receive study assessments. Serial blood samples will be obtained at defined time points within 7 days after dosing in each treatment for the measurement of plasma (S)amlodipine and (R)amlodipine concentrations. After a wash-out period for at least 14-days since the last dosing, subjects will enter into Period 2 to receive alternative reference or test drug. The same procedure will be performed at approximately same time points as noted for Period 1.

Part 2 will be a single-arm, open-label, single-dose phase to assess food effect on the PK profile of levamlodipine maleate tablets from CSPC. Subjects who have completed Part 1 will be rolled over to Part 2 after a wash-out period for at least 14-days since the last dosing. Subjects will receive a single oral administration of 5 mg levamlodipine maleate tablets from CSPC under a highfat/high-calorie meal that should derive approximately 150, 250 and 500-600 calories from protein, carbohydrate and fat, respectively. Subjects will be admitted to the clinical research center (CRU) within 24 hours before drug administration and will stay at the CRU for 3 nights. Subjects should return to the CRU on Days 4 till 8 to provide PK samples and to receive study assessments. Serial blood samples will be obtained at defined time points for the measurement of plasma (S)amlodipine and (R)amlodipine concentrations.

Safety and tolerability will be monitored during the study.

1.3 Sample Size Estimation

Based on an approximate CV_B of 20%, a CV_W is calculated to be 14% for C_{max} and 11% for AUC_{0-inf}, respectively. Thus, an N value of approximately 18 completed subjects for AUC (%CV rounded off to 10%), an N value (interpolated) of approximately 27 completed subjects would be required for the proposed bioequivalence study. With an estimated drop-out rate of 20% in this cross-over study, approximately 32 subjects will be enrolled.

1.4 Randomization

In Part 1, subjects will be assigned in a ratio of 1:1 to receive one of two treatment sequences (RT or TR; R=10 mg of NORVASC® and T=5 mg of levamlodipine maleate tablets). Each sequence will have 16 subjects randomized for a total of 32 patients. {The text presented in this section had been edited from that in Section 8.1 of the protocol. See Section 8 of this SAP for further details}

1.5 Study Data

The study data to be analyzed include all clinical data captured by the case report form (CRF), including safety lab data. The CRF database will be locked for the final analyses.

2 GENERAL ANALYSIS DEFINITIONS

All analysis dataset preparations and statistical analyses will be performed using SAS® version 9.4 or higher. No imputation will be performed for missing data unless stated otherwise. Listings for CSR Appendix 16.2 will include all the subject data points being collected or derived for analyses. Data listings will be provided for all subjects up to the point of withdrawal.

2.1 Study Parts and Treatment Sequences/Groups

For analyses per randomized, the two randomized treatment sequences will be labelled as "Levamlodipine, Then NORVASC" and "NORVASC, Then Levamlodipine". For analysis per treated, the two actual treatment groups will be labelled as Levamlodipine and NORVASC. The two study parts will be labelled as "Study Part 1" and "Study Part 2".

2.2 Statistical Hypothesis Tests

No statistical hypothesis tests will be performed for the analyses described in this SAP. The bioequivalence data does have associated hypothesis testing which is detailed in a separate analysis plan for PK analyses.

2.3 Study Periods, Visit, and Day

The overall study consists of initial screening and three treatment periods, separated by two wash-out periods between treatment periods. Each treatment period includes a 3-day visit admitted in the CRU, followed by 5 daily visits. A reference date refers to the start date of the study drug administration for each treatment period. All efficacy and safety assessments at all visits will be assigned a day relative to this date within each treatment period. The relative day will be defined as: visit date – reference date + 1 for visits on or after the reference date, and visit date – reference date for visits before the reference date. Consequently there is no 'Day 0' defined.

In general, the baseline is defined as the last assessment before the intake of the first study medication during each treatment period unless specifically stated otherwise. All scheduled assessments after first administration of study drug will be used. Repeat/unscheduled assessments will not be used in descriptive statistics or any per-time point analysis, but will be shown in listings as applicable. Pre-dose unscheduled assessments will be taken into account for baseline determination and post first dose unscheduled assessments will be taken into account for worst-case determination as applicable.

2.4 Analysis Populations

2.4.1 Screened Population

All subjects who were screened and signed the informed consent are included in the Screened Population (SCRN).

2.4.2 Randomized Population

All randomized subjects are included in the Randomized Population (RAND).

2.4.3 Safety Population

All safety endpoints will be evaluated on the Safety Population (SAF), consisting of all subjects who received at least one dose of study drug and will be analyzed by the treatment group as treated.

2.4.4 Pharmacokinetic Population

The Pharmacokinetic Population is documented in a separate analysis plan for PK analyses. It is not applicable to the analyses described in this statistical analysis plan.

All protocol deviations that occur during the study will be considered for their severity/impact and will be taken into consideration when subjects are assigned to analysis populations prior to final database lock.

A summary table of number (%) of patients in each analysis population/set will be provided (Table 14.1.1).

2.5 Definition of Subgroups

No subgroup analyses are planned.

2.6 Descriptive Summaries

Summary statistics and statistical analyses will generally only be performed for subjects included in the relevant analysis population. For the calculation of summary statistics and statistical analysis, unrounded data will be used. All tabulated summaries will include two Study Parts and Treatment Sequences/Groups. For endpoints that are continuous in nature: number of observations, mean, median, minimum and maximum, and standard deviation (SD) values will be presented as descriptive summary. For endpoints that are categorical in nature: frequency counts and percentages will be presented as descriptive summary.

The number of decimal places to display for calculated data will be determined by the original scale of the data. Means and medians will be reported with one (1) additional decimal place. Standard deviation will be reported with two (2) additional decimal places. Minimum and maximum will be reported with the same number of significant digits as the method of capture.

3 PLANNED INTERIM ANALYSIS

No interim analyses are planned.

4 SUBJECT INFORMATION

In general, all subject-level parameters will be summarized for the Randomized Population based on randomized treatment sequence group, unless stated otherwise.

4.1 Disposition Information

Summaries will be provided for the following disposition information: Number of subjects screened, screening failures, randomized, completed Part 1, and completed or discontinued study with the reasons of discontinuation. The reasons of discontinuations include following categories:

- Adverse Event
- Subject Requested Withdrawal
- Investigator Decision
- Sponsor Decision
- Subject Lost to Follow-up
- Subject Died
- Pregnancy
- Other

The randomized treatment sequence group will be shown for Randomized Population (Table 14.1.2).

4.2 **Protocol Deviations**

All reported major protocol deviations and determined exclusions from any analysis population(s) will be documented and included in the CSR.

4.3 Demographics and Baseline Characteristics

Descriptive statistics or frequency tabulation will be provided for the following parameters.

4.3.1 Demographic Parameters

Descriptive statistics or frequency tabulation will be provided for following parameters (Table 14.1.3.1):

- Age (years): continuous and categorized as 18-40 years and 41-45 years
- Sex (Male, Female)
- Race (White, Black or African American, Others for all other race categories captured on CRF)
- Ethnicity (Hispanic or Latino, Not Hispanic or Latino)
- Weight at baseline (kg)
- Height at baseline (cm)
- Body Mass Index (BMI) at baseline = Weight at baseline (kg) / [Height at baseline (m)]² (rounded to 1 decimal. Although available in the raw data, BMI will be recalculated from last weight and height measurement before start of treatment)

4.3.2 Tobacco and Alcohol Use

Descriptive statistics or frequency tabulation will be provided for the following parameters related to tobacco or alcohol use (Table 14.1.3.2):

- Smoking status (Never Smoked, Current Smoker, Ex-Smoker)
- Used tobacco in past 6 months (Yes, No)
- Had alcohol in past 6 months (Yes, No)
- Average number of drinks per week

4.4 Medical History

All reported medical history will be coded by Medical Dictionary for Regulatory Activities (MedDRA, version 20.0), and summarized by MedDRA system organ class and preferred term, in order of descending overall frequency for the Randomized Population (Table 14.1.4).

4.5 **Prior and Concomitant Medications**

All reported medications will be coded using the World Health Organization-Drug Dictionary (WHO-DD, version September 2018) and summarized separated for each of following two categories:

- Prior medication: medication received during the 4 weeks (30 days) prior to Screening but is no longer taking, collected on the CRF page "Prior Medication" at screening.
- 2) Concomitant medication: medication received during the study, collected on the CRF page "Concomitant Medication".

Prior medications will be included in the subject data listing (Listing 16.2.5.1). A frequency tabulation for concomitant medications will be shown by WHO-DD ATC class level 4 and preferred term for the Safety Population (Table 14.1.5).

4.6 Extent of Exposure

Frequency tabulation will be provided for the number and percentage of subjects exposed within each treatment period for the Safety Population (Table 14.1.6).

5.1 Adverse Events

5.1.1 Coding of Adverse Events

The verbatim terms of adverse events (AEs) will be coded using the Medical Dictionary for Regulatory Activities (MedDRA, version 20.0). Events are summarized by system organ class and preferred.

5.1.2 Treatment-Emergent AE

Pre-treatment AEs are defined as AEs that were reported or worsened after signing the ICF up to the start of first study drug dosing. Treatment-emergent AEs (TEAE) are defined as AEs that were reported or worsened on or after the start of study drug dosing and before the start of subsequent drug dose (Treatment Periods 1 and 2) or up to and including the end of the follow-up phase (Treatment Period 3).

5.1.3 Phase Allocation of TEAE

Adverse events are allocated to phases based on their start date and time. If the start date and time of an event falls between (or on) the start and stop date and time of a phase, the TEAE is attributed to that phase (treatment-emergent principle).

Rule: phase start datetime ≤ TEAE start datetime ≤ phase stop datetime.

In case of partial AE start dates and or times, the events are allocated to the phases using the available partial information on start and end datetime; no imputation will be done. If, for instance, for the AE start date only month and year are available, these data are compared to the month and year information of the phases. This rule may lead to multiplication of the event as a consequence of its assignment to multiple phases. In case of a completely missing AE start date, the event is allocated to the first treatment phase, except if the end date of the AE falls before the start of this treatment phase. In case of any other missing scenarios, the phase allocation of AE will be determined by manual data review prior to database lock.

5.1.4 Variables Attributed to Adverse Events:

- AE term (verbatim and MedDRA preferred term and system organ class)
- Start datetime, End datetime, and duration of AE
- Frequency (Single Episode, Intermittent, Continuous)
- Serious AE (Yes/No), if yes classification will be listed
- Severity (Mild, Moderate, Severe)
- Relation to study treatment (Not related, Possibly Related, Probably Related)
- Action taken with study treatment (No Action Taken, Non-Drug Therapy, Medication Given, Discontinued, Other)
- Outcome of AE (Recovered/Resolved, Resolved/Resolved with Sequelae, Recovering/Resolving, Not Recovered/Not Resolved, Fatal, Unknown)

5.1.5 Analysis Methods

There will be no formal statistical testing unless indicated otherwise. A summary will be provided for the following TEAEs for each treatment within each study part (Part 1 and 2) (Table 14.3.1.1):

- any AE
- any AE at least possibly related to study medication
- any serious AE
- any AE leading to early withdrawal
- any AE leading to death

The adverse events will be shown by MedDRA system organ class and preferred term, in order of descending overall frequency. For each AE, the percentage of subjects who experience at least 1 occurrence of the given event will be summarized for each treatment within each study part. Incidence tabulations will be provided for overall summary (Table 14.3.1.2), summary by highest severity (Table 14.3.1.3), and summary by relatedness (Table 14.3.1.4).

5.2 Clinical Laboratory Evaluations

Numeric measurements of hematology, blood chemistry and urinalysis will be evaluated. Following parameters will be reported:

Hematology

- Hemoglobin (Hgb)
- Hematocrit (Hct)
- Platelet count
- Red blood cell (RBC) count
- White blood cell (WBC) count with differential

Clinical Chemistry

- Blood urea nitrogen (BUN)
- Creatinine
- Total bilirubin
- Alkaline phosphatase
- Aspartate transaminase (AST)
- Alanine transaminase (ALT)
- Gamma-glutamyl transferase (GGT)
- Lactic dehydrogenase (LDH)
- Glucose
- Albumin
- Total protein
- Bicarbonate
- Phosphate
- Sodium
- Potassium
- Chloride
- Calcium
- Total cholesterol
- Urate

Urinalysis

■ pH

- Specific gravity
- Protein
- Glucose
- Ketones
- Bilirubin
- Blood
- Nitrites
- Leukocytes
- Urobilinogen
- Microscopic urine analysis

Actual values of numerical lab results and changes from baseline will be summarized at Day 8 for each treatment within each study part (Table 14.3.2.1.1-

14.3.2.1.3). Shift tables from the baseline to Day 8 will be presented (Table 14.3.2.2.1-14.3.2.2.3). Categorical lab results will be included in the subject data listing (Listing 16.2.8).

5.3 Vital Signs

Summary statistics will be presented for the actual values and change from baseline values (as appropriate) at each collected time point for all vital signs measured at sitting position: Oral Temperature (Celsius), Heart Rate (bpm), Systolic Blood Pressure (mmHg), Diastolic Blood Pressure (mmHg), Respiratory Rate (breaths/min). Changes from baseline for blood pressures and heart rate will include Days 1, 2, 3, 4, 5, 6, 7, and 8, and changes from baseline for oral temperature and respiratory rate will include Days 1, 2, 5, and 8 for each treatment within each study part (Table 14.3.3).

5.4 Electrocardiogram

P-R interval (msec), QT interval (msec), QRS duration (msec), Ventricular heart rate (beats/min), QTcB intervals (msec) using Bazett's correction formula, and QTcF intervals (msec) using Fridericia's correction formula will be collected on CRF. The mean values of triplicate ECG assessments prior to dosing will be used as the baseline. Actual values and changes from baseline will be summarized at each scheduled timepoint (Day 8) for each treatment within each study part (Table 14.3.4.1). In addition, frequency tabulation of the overall ECG results (Normal, Abnormal NCS, and Abnormal CS) will be summarized (Table 14.3.4.2).

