Subjects will be admitted to the clinical research center (CRU) within 24 hours before drug administration and will stay at the CRU for 3 nights. Subjects should return to the CRU on Days 4 till 8 to provide PK samples and to receive study assessments. Serial blood samples will be obtained at defined time points for the measurement of plasma (S)amlodipine and (R)amlodipine concentrations.

Safety and tolerability will be monitored during the study.

	Screening		Clinical Resear	Clinical Visits						
Day	(Day -21 to -1)	Day 0 ¹ (Baseline)	Day 1 (Dosing)	Day 2	Day 3	Day 4	Day 5	Day 6	Day 7	Day 8
Informed consent	X									
Medical history	X									
Physical examination ²	Х									Х
Vital signs ³	X	Х	Х	X	Х	Х	Х	Х	Х	Х
12-lead ECG	X	X ⁴								Х
Clinical safety tests	X ⁵	Х								Х
Drug/alcohol test	Х	Х								Х
Pregnancy test ⁶	Х	Х								
Admission to CRU		Х								
Randomization			Х							
Dose administration			Х							
PK blood samples ⁷			Х	X	Х	Х	Х	Х	Х	Х
AE & ConMed		Х	Х	X	Х	Х	Х	Х	Х	Х
Discharge from CRU					Х					

 Table 5-1.
 Schedule of Procedures for Part 1 - Period 1

¹ Baseline.

² Including body weight and height at screen only.

³ Complete vital sign measurements at screening visit, Day 0 and 0, 24, 96 and 168 hours after dosing. Blood pressure and heart rate only at other time points. Three measurements

of blood pressure at screening visit and a single measurement at other time points.

⁴ Three ECG tests with 3 min interval in between on Day 0. The means of the three ECG tests will be used as baselines.

⁵ HIV, hepatitis B & C screen test at screening visit only.

⁶ Serum test at screening and urine test on Day 0 for females of childbearing potential only.

⁷ Pharmacokinetic blood samples will be collected at the following time points: Pre-dose (within 30 min prior) and at 1, 2, 3, 4, 5, 6, 7, 8, 9, 10, 11, 12, 14, 16, 24, 36, 48, 72, 96,

120, 144, and 168 hours after dosing (acceptable windows: ± 2 min for 0 to 2-hr post dose period and ± 5 min thereafter)

AE = adverse event; ConMed = concomitant medications; CRU = clinical research unit; ECG = electrocardiogram; PK = pharmacokinetics.

Confidential

	Wash-out	Clini	ch Unit (Cl	Clinical Visits						
Day	At least 14 days since the last dosing	Day 0 (Admission)	Day 1 (Dosing)	Day 2	Day 3	Day 4	Day 5	Day 6	Day 7	Day 8
Admission to CRU		Х								
Cross-over of treatment		Х								
Physical examination		Х								Х
Vital signs 1		Х	Х	Х	Х	Х	Х	Х	Х	Х
12-lead ECG		Х								Х

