7.1.2. Baseline (Day 0)

Subjects will be admitted to the CRU on Day 0 and remain sequestered at the CRU until the collection of the PK sample of 48 hours after dosing.

On arrival at the clinical research unit, all subjects will undergo the following assessments:

- Vital signs including blood pressure, heart rate, respiratory rate and temperature
- Three 12-lead ECGs will be recorded with 3-min interval at this visit. The means of the three ECGs will be used as the baselines.
- Overnight fasting blood sample collection for safety tests
- Drug/alcohol test
- Urine pregnancy test for females of childbearing potential
- Admission to the CRU for eligible subjects
- Assessment of AEs and concomitant medications

Enrolled patients will be fasted from 10 pm the day prior to dosing until approximately 4 hours after administration the next day (dosing day). Water intake will be permitted until 6 am of the dosing day.

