7.2.1. Admission (Day 0)

The following assessments and procedures will be performed and documented:

- Admission to CRU
- Cross-over to treatment
- Physical examination
- Vital signs
- A single 12-lead ECG record
- Overnight fasting blood sample collection for safety tests
- Drug/alcohol test
- Urine pregnant test for females of childbearing potential
- Assessment of AEs and concomitant medications.

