7.3. Part 2 (Food Effect)

7.3.1. Admission (Day 0)

Subjects who have completed Part 1 will be rolled over to Part 2 after a wash-out period for at least 14-days since the last dosing to assess food effect on the PK profile of levamlodipine maleate tablets from CSPC. Eligible subjects will be admitted to the CRU on Day 0 and remain sequestered at the CRU until the collection of the 48-hour PK sample after dosing.

On arrival at the clinical research unit, all subjects will undergo the following assessments:

- Physical examination
- Vital signs including blood pressure, heart rate, respiratory rate and temperature
- A single 12-lead ECG
- Overnight fasting blood sample collection for safety tests
- Drug/alcohol test
- Urine pregnancy test for females of childbearing potential
- Admission to the CRU
- Assessment of AEs and concomitant medications

Enrolled patients will be fasted from 10 pm the day prior to dosing until approximately 4 hours after administration the next day (dosing day). Water intake will be permitted until 6 am of the dosing day.

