12.7. Safety Analyses

Safety evaluations will be based on the incidence, intensity, and relatedness of AEs and changes in subjects' physical examination findings, ECGs, vital signs, clinical laboratory results. Safety variables will be tabulated and presented for all subjects in the Safety Population. Data will be summarized by treatment. Adverse events will be coded using the Medical Dictionary for Regulatory Activities (MedDRA) for preferred term and system organ class, listed by subject. Treatment-emergent AEs (TEAEs) will be summarized by treatment, where treatment-emergent is defined as any event not present prior to the initiation of the treatments or any event already present that worsens in either intensity or frequency following exposure to the treatments. All AEs will be summarized by relationship to study drug and by intensity.

Deaths, SAEs, and AEs resulting in study discontinuation will be tabulated and detailed in narratives.

If adequate data are available, an analysis will be performed for PK profile (e.g., T_{max}) in conjunction with time to occurrence of adverse events.

Change from baseline, defined as time of admission to the CRU (Day 0), in clinical laboratory parameters, 12 lead ECGs, and vital sign parameters will be summarized by treatment and study period.

Additional safety analyses may be defined in the Statistical Analysis Plan.

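### Does SAP 5.4 leave the ECG baseline undefined in Part 1 Period 2 and in Part 2, where only one pre-dose ECG is scheduled?

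*SAP*

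**What the plan says.** SAP 5.4 sets the ECG baseline in one sentence, with no limit to any period: "The mean values of triplicate ECG assessments prior to dosing will be used as the baseline". It then asks for a summary that spans all three dosing periods: "Actual values and changes from baseline will be summarized at each scheduled timepoint (Day 8) for each treatment within each study part".

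The protocol's ECG schedule differs by period:

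- Part 1 Period 1: "Three ECG tests with 3 min interval in between on Day 0" (Table 5-1, footnote 4) and "Three 12-lead ECGs will be recorded with 3-min interval at this visit" (Protocol 7.1.2). Both places add that the mean of the three is the baseline.
- Part 1 Period 2: "A single 12-lead ECG record" (Protocol 7.2.1).
- Part 2: "A single 12-lead ECG" (Protocol 7.3.1).

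Tables 5-2 and 5-3 have no triplicate footnote.

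Two general rules also bear on the point. In SAP 2.3, "the baseline is defined as the last assessment before the intake of the first study medication during each treatment period", subject to any specific rule elsewhere in the SAP. Protocol 12.7 takes baseline as admission to the unit on Day 0, names 12-lead ECGs among the variables covered, and summarizes by treatment and study period.

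**The concern.** The rule and the schedule do not match. A rule that needs three tracings can be met within period on one of three dosing occasions, and never in Part 2. SAP 2.3 gives way to specific rules and SAP 5.4 is one, so a literal reader could conclude that the general rule has been switched off for ECGs. Two unwelcome readings would then be open.

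- The change from baseline is missing in Period 2 and Part 2.
- The Period 1 mean serves as baseline throughout.

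Under the second reading, Part 2 changes would be measured from a value two doses old. At least 14 + 14 = 28 days separate Period 1 dosing from Part 2 dosing, so any drift over that time would enter the change. SAP 5 pools the two Part 1 phases by actual treatment, so the Part 1 rows would mix same-period and older baselines. Two programmers could then fill Table 14.3.4.1 differently from the same data.

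A smaller point arises for vital signs. On dosing days, temperature and respiratory rate are taken only before the dose (Protocol 7.1.3, 7.2.2 and 7.3.2). Under SAP 2.3 that reading is itself the baseline, so the Day 1 change that SAP 5.3 lists for these two variables is zero by construction.

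**Working it through.** The plan gives no figure to reproduce here. The check is a reading of the rules against the schedule, followed by a small variance calculation.

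**1. Pre-dose ECGs available**

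| Dosing period | Scheduled pre-dose ECGs | Source |
|---|---|---|
| Part 1 Period 1 | 3 | Table 5-1 footnote 4; Protocol 7.1.2 |
| Part 1 Period 2 | 1 | Table 5-2; Protocol 7.2.1 |
| Part 2 | 1 | Table 5-3; Protocol 7.3.1 |

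Every period has at least one, so an own-period baseline always exists by design. With 32 subjects and no dropout, 2 × 32 = 64 of 3 × 32 = 96 dosing periods lack a triplicate. That count describes the schedule. It does not measure error, because each of the 64 has its own admission ECG.

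**2. What SAP 5.4 adds to SAP 2.3**

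Under SAP 2.3 alone, the Period 1 baseline would be the last of the three tracings. SAP 5.4 replaces that with their mean, as Table 5-1 and Protocol 7.1.2 already say. The exception is therefore needed only where replicates exist. It says how to reduce three readings to one; it does not say that baseline stops being specific to the period.

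**3. The three readings tested**

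- *Change missing in Period 2 and Part 2.* This defeats SAP 5.4 itself, which asks for changes in each study part. Part 2 would be empty.
- *Period 1 mean carried forward.* No sentence says so. It conflicts with the per-period anchor in SAP 2.3 and with the by-period summary in Protocol 12.7. Borrowing a value from an earlier period also sits badly with SAP 2, which allows no imputation unless stated.
- *Own-period baseline.* The triplicate mean is used in Period 1 and the single admission ECG afterwards. This agrees with SAP 2.3 and Protocol 12.7, and fills every cell that SAP 5.4 requests.

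Only the third reading is consistent with all the text.

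**4. Balance in Part 1**

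SAP 1.4 puts 16 subjects in each sequence. With no dropout, each treatment's Part 1 row has 16 baselines from a triplicate mean and 16 from a single ECG. The mix is the same for both treatments, so it favours neither.

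**5. Precision cost of a single baseline ECG**

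Assume replicate variance s² within a visit and between-day variance k·s², with a single ECG on Day 8.

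- Variance of change with a triplicate mean: s²(2k + 1 + 1/3) = s²(2k + 4/3).
- Variance of change with a single ECG: s²(2k + 2).
- SD ratio: √[(2k + 2)/(2k + 4/3)].

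| k (assumed) | SD ratio |
|---|---|
| 0 | √(2/1.333) = 1.22 |
| 1 | √(4/3.333) = 1.10 |
| 4 | √(10/9.333) = 1.04 |
| large | tends to 1 |

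The documents do not give k, so the range is 0% to 22%, and the top of it requires no day-to-day variation at all. Averaging more tracings changes the spread of the change, not its expected value. This cost comes from the protocol's schedule, and another sentence in the SAP would not remove it.

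**6. Vital signs**

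The Day 1 change for temperature and respiratory rate is zero under the SAP 2.3 baseline and need not be zero under the Day 0 baseline of Protocol 12.7. The two rules do differ here. SAP 1 gives the SAP precedence over the protocol's statistical text, and SAP 5.3 already limits change summaries to where they make sense. A row of zeros alters no conclusion. Deleting it would settle the choice between the two baselines without reconciling them.

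**The case for a change.** The best case for a change runs as follows. SAP 2.3 yields to specific rules, SAP 5.4 is specific, and nothing says that the general rule returns where no triplicate exists. Protocol 12.7 cannot settle the matter alone, because the SAP supersedes the protocol's statistical text. The carry-forward reading has some support: Table 5-1 labels Day 0 as baseline, while Tables 5-2 and 5-3 label it as admission, and Protocol 11.1.4 ties the three ECGs to baseline without naming a period. Protocol 7.2 also says that Period Two repeats the Period One procedure. SAP 7 lists only the randomization wording as a change from the protocol. A clarifying sentence would cost almost nothing.

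What stands is that SAP 5.4 is incomplete as worded and does not spell out the single-ECG case. The rest is weak. Column labels and a general statement about repeating procedures do not outweigh visit lists that specify one ECG, or a baseline rule written for each treatment period. The mock shells that guide programming are a separate document (SAP 1) and cannot be seen here, so it is not known whether any doubt would survive into programming. The drift and mixed-age baselines arise only under carry-forward, which no sentence prescribes.

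**Conclusion.** No change is needed. The gap is one of wording, and the SAP's own general rule fills it: the mean of the three tracings in Period 1, and the single admission ECG in Period 2 and Part 2. The remaining effect is a change-from-baseline SD that is 0% to 22% larger where a single ECG is used, spread equally over the two Part 1 treatments. It is confined to Table 14.3.4.1, a descriptive safety table in an SAP that plans no hypothesis tests (SAP 2.2). The pharmacokinetic results, the bioequivalence limits and the sample size do not depend on it.

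This rests on three assumptions: the admission ECGs are obtained as scheduled, the period-specific visit lists govern the number of tracings, and sequence sizes stay close to 16 and 16. The vital-sign row does not alter the conclusion, since a Day 1 change of zero for temperature and respiratory rate is uninformative but harmless.
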